7.3. Risk Minimization

Additional risks may exist. Risks can be minimized through the use of strict compliance with this CIP, and adherence to the guidelines for Subject selection, site training, and close monitoring of the Subject's physiologic status at follow-up visits. In addition, the product labeling (including the Implant and Programming Manual and the User Manual) details warnings and precautions which must be followed to minimize risk to Subjects.

8. Safety

The following definitions are used:

Adverse Event (AE):

An adverse event is defined as any undesirable clinical occurrence that affects the health or safety of the Subject.

If an adverse event leads to multiple outcomes that sequentially worsen, only the worst adverse event is reported. For example, a hematoma leading to infection would be reported as a single AE for the infection.

Serious Adverse Event (SAE):

A Serious Adverse Event is defined as an adverse event that led to death, or led to serious deterioration in the health of the Subject, that either resulted in:

1. a life-threatening illness or injury, or
2. a permanent impairment of a body structure or a body function, or
3. in-patient or prolonged hospitalization,
4. congenital anomaly/birth defect, or
5. medical or surgical intervention to prevent life-threatening illness or injury or permanent impairment to a body structure or a body function.

Note: Planned hospitalization for a pre-existing condition or a procedure required by the protocol (e.g., the index implant procedure, or device replacement due to normal battery depletion), without serious deterioration in health, is not considered a serious adverse event.

Unanticipated Adverse Device Effect (UADE):

An unanticipated adverse device effect means any serious adverse effect on health or safety or any life-threatening problem or death caused by or associated with a device, if that effect, problem, or death was not previously identified in nature, severity, or degree of incidence in the investigational plan or application, or any other unanticipated serious problem associated with a device that relates to the rights, safety, or welfare of Subjects.

For all adverse events the Investigator must determine whether the event was related to the device and/or procedure and document this on the eCRF. Individual events may be related to more than one category, e.g. an injury due to a tunneling tool may be related to Device Hardware and Procedure. The categories used for relatedness are listed in Table 4.

Table 4: Adverse Event Relatedness Categories

Related to Device Hardware	Events reasonably anticipated to be related to the physical presence of the device, e.g. erosion, a device deficiency, loss of power.
Related to Device Stimulation	Events reasonably anticipated to be related to electrical stimulation, especially those that appear when the device is on and disappear when the device is off, e.g. undesired sensation experienced only when the device is turned on.
Related to Procedure	Events reasonably anticipated to be related to procedures described in this protocol.

All AEs will be collected from the time of informed consent through the end of the study. Death should not be recorded as a separate adverse event, but rather as an outcome of the specific SAE which led to the Subject's death.

Adverse Events that would be reasonably expected to be associated with any surgical procedure (e.g.: anesthesia associated nausea, surgical site pain) will not be categorized as procedure or device related in the 30 days post the surgical procedure (to be adjudicated by the Adjudication Committee).

The Adjudication Committee will review and adjudicate all Adverse Events that occur, including relatedness. The Committee will also review and adjudicate all reported hospitalizations, regardless of whether they are classified by the Investigator as an adverse event. Safety Analysis will be performed on adjudicated events only.

Notes:

1. Any current condition that is recorded as a pre-existing condition is not an AE, unless there is a worsening of that condition in terms of nature, severity, or degree of incidence.
2. Technical observations – an undesirable device event that does not result in a medically undesirable situation for the Subject – is not an AE.
3. Normal end of battery life of the IPG is not an AE.
4. Suspending or stopping use of ReActiv8 due to pain relieved is not an AE.
5. ReActiv8 removed due to pain relieved is not an AE.
6. Planned hospitalization for a procedure required by this protocol is not an AE. However, complications during the course of that planned hospitalization that prolong the anticipated duration of the hospitalization do constitute SAEs.
7. Elective hospitalization for a pre-existing illness does not constitute an SAE unless the illness has worsened in the nature, severity or degree of the condition with respect to baseline.
8. Device migration will not be collected as an AE, but rather as a device deficiency. If device migration results in a clinical symptom, report this as an AE in addition to the device deficiency report documenting device migration.
9. Experiencing unusual sensations is a normal part of programming a neurostimulation device. Accordingly, symptoms felt during a programming session are not considered AEs unless they are caused by the final programming parameters and persist after completion of the programming session.
10. Lack of efficacy or diminished therapeutic response does not constitute an AE since failure to receive therapeutic benefit is an issue of efficacy, not safety. This includes symptoms that recur in the context of device deficiency leading to loss of therapy. If the recurring symptoms are not worse than at baseline, record the event as a device deficiency but not as an adverse event.
11. Removal and/or replacement of any part of the device due to malfunction would be considered a device related adverse event.

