8.2. Adverse Event Outcome Status

Adverse Events, when reported, are assigned a status by centers depending on the nature of the event or the corrective action involved. When clinically appropriate, centers should work to close events whose underlying clinical condition may not be resolvable during the term of the investigation.

Centers may move outcome status to “closed” or alternatively, add text to the adverse event description at a follow-up visit addressing that adverse event stating that the adverse event is ongoing but for study purposes and outcome data, the event is considered closed.

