9.1.14. Adverse Events

All transient and long-term adverse events will be collected throughout the course of the study. Assessment will include Investigator-assessed relationship to device, relationship to procedure, severity (i.e.: AE or SAE), subsequent treatment/intervention required and resolution status at each follow-up visit until the event is resolved or closed because of chronic nature of the event. Note that a Subject death automatically closes any outstanding adverse events for that Subject.

Collection Method: Paper CRF or eCRF

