8.8. Safety Analysis

8.8.1. Primary Safety Assessment

The primary safety assessment is of serious device and/or procedure related adverse events in all Subjects in the Intent to Treat Cohort at the Primary Endpoint Assessment Visit. All reported adverse events will be documented and reported with summary statistics presented for observed rates. There are no formal, statistical hypotheses being tested in the safety assessment.

There will be a separate safety analysis of Subjects in the Surgical Roll In Cohort. If numbers permit, a Poolability analysis of the ITT and the Surgical Roll In Cohort will be conducted.

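### The worst-event-only rule in Protocol Section 8 drops complications that progress, conflicts with the promise to collect all adverse events, and lowers event counts and event-type rates by an unknown amount

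*Protocol*

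**What the plan says.** The Adverse Event definition in Protocol Section 8 contains this rule: "If an adverse event leads to multiple outcomes that sequentially worsen, only the worst adverse event is reported". It is illustrated directly afterwards: "For example, a hematoma leading to infection would be reported as a single AE for the infection".

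Two other places promise full collection. Later in Section 8: "All AEs will be collected from the time of informed consent through the end of the study". In Section 9.1.14: "All transient and long-term adverse events will be collected throughout the course of the study". Section 8.1 adds that all adverse events will be reported to Investigators and ethics bodies.

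Section 8 restricts the safety analysis to adjudicated events. SAP 8.8.1 makes serious device- or procedure-related events in the ITT Cohort at the Primary Endpoint Assessment Visit the primary safety assessment, with no hypothesis test. It continues: "All reported adverse events will be documented and reported with summary statistics presented for observed rates".

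On outcome status, Section 8.2 says that, when clinically appropriate, "centers should work to close events whose underlying clinical condition may not be resolvable during the term of the investigation". A site may either set the status to closed or add text saying that "the adverse event is ongoing but for study purposes and outcome data, the event is considered closed".

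**The concern.** A hematoma in the operated area fits the opening sentence of the Adverse Event definition by itself, and Section 7.2 names hematoma and infection among the anticipated events. The worst-only rule removes it once it has led to something worse. What is lost is therefore selective: the complications that progressed go, and those that settled stay.

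Later steps are unlikely to recover it. A precursor that was never reported would not normally reach the Adjudication Committee, and the SAP summarises only what was reported.

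Because no safety hypothesis is tested, the descriptive rates are the whole safety result, and the rule for what counts as an event determines them. The definition of an unanticipated adverse device effect also refers to degree of incidence, so incidence by type has a use beyond the tables. If some sites follow the worst-only rule and others follow Section 9.1.14, the rates will also differ by site for reasons unrelated to the device.

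**Working it through.** Neither document states a safety rate, an event count or a progression fraction, so there is no figure of the plan to reproduce. The check is a reading of the text plus an illustration.

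**Step 1. Do the instructions agree?** Take a Subject with a hematoma that leads to an infection.
- Section 8, worst-only rule: one record, an infection.
- Section 8 (collection statement) and Section 9.1.14: both events are collected, since both are clinical occurrences and 9.1.14 expressly covers transient ones.

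A site cannot satisfy both on their plain reading.

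**Step 2. Effect on the rate of an event type.** Let p be the true incidence of an event type that can start a chain, and f the share that progresses to a worse event coded as another type. With at most one such event per Subject:

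reported rate = p × (1 − f); events lost among N Subjects = N × p × f.

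N = 128 is the planned ITT Cohort (Protocol 4.4). The values of p and f are assumptions.

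| p | Events occurring (128 × p) | f | Events reported | Reported rate |
|---|---|---|---|---|
| 5% | 6.4 | 10% | 5.8 | 4.5% |
| 5% | 6.4 | 25% | 4.8 | 3.75% |
| 5% | 6.4 | 50% | 3.2 | 2.5% |
| 10% | 12.8 | 10% | 11.5 | 9.0% |
| 10% | 12.8 | 25% | 9.6 | 7.5% |
| 10% | 12.8 | 50% | 6.4 | 5.0% |

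For example, 128 × 0.10 × (1 − 0.25) = 9.6. Over the grid, the loss runs from 128 × 0.05 × 0.10 = 0.64 events to 128 × 0.10 × 0.50 = 6.4 events. The relative understatement is f whatever the value of p.

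**Step 3. Effect on Subject-level counts.**
- Subjects with any adverse event: unchanged, because each chain still yields one record.
- Subjects with a serious related event, the primary safety measure:
  - Precursor not serious, retained event serious and related: the Subject is counted.
  - Both serious and related: the Subject is counted, but two serious events become one.
  - Precursor serious and related, retained event adjudicated unrelated: the Subject is lost.
  - Chain running across the 120-day visit: undetermined, because no section says which date the single record carries.

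**Step 4. Closure.** Closing an event does not remove it from incidence. Section 9.1.14 follows status until an event is either resolved or closed as chronic, so it names two end states. Section 9.4 ends follow-up of adverse events after a failed implant at either one. SAP 8.8 plans no table by outcome status. Section 8.2 therefore affects a result only if someone later tabulates closed events as resolved, which its wording about outcome data leaves open.

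**The case against.** The best defence is that the worst-only rule is openly stated, illustrated, and placed inside the definition, so that collecting all adverse events means collecting all events as so defined. It resembles the rule that death is recorded as the outcome of the event that caused it. Subjects with a progressing complication are not lost; they appear under the more severe event. All reported events are independently adjudicated, as are all reported hospitalizations whether or not the site called them adverse events, so some serious precursors could surface that way. The case report forms are not among the documents and may already hold onset or linkage fields.

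Much of this stands as a limit on the point, but it does not remove it. The reading by definition leaves the transient events promised in 9.1.14 unexplained, and a hematoma that became an infection is still absent from the hematoma rate.

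A reader might infer several stronger claims that the documents do not support:
- That rates of early complications in general are understated. Those that do not progress are still reported.
- That the primary safety measure is materially biased. It is affected only in the two situations in Step 3.
- That the single record takes the later onset date. No section assigns a date.
- That unresolved harm is understated. Closed events stay in incidence, 9.1.14 distinguishes closed from resolved, and no unresolved-event count is planned.
- That time-to-onset, persistence or labelling results are distorted. The SAP plans none of these.

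**Conclusion.** The point holds in a limited form. Following the worst-only rule lowers the total event count and the rate of any event type that can precede a worse one, by exactly the fraction that progresses. The direction follows from the rule and from the protocol's own example. The size is unknown, because incidence and progression both have to be assumed; over the ranges tried, the loss is between fewer than one and about six events of a given type in 128 Subjects. This rests on one such event per Subject and on sites following the rule as written.

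The conflict between the definition and the two collection statements needs no assumption and should be reconciled. The closure wording is a secondary matter: a possible masking of ongoing harm in an outcome table that is not yet planned. Efficacy and sample size are unaffected. This is a cheap improvement to descriptive safety reporting and does not show that the main safety result is wrong.

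**What to change.** - **Protocol Section 8:** replace the worst-only rule. Record each clinically distinct event with its own onset, seriousness and relatedness, and a link to the event it followed. Note 8 of the same section already asks for paired records when a device migration causes symptoms, so the approach is familiar to sites.
- **Protocol Sections 8 and 9.1.14:** reconcile the definition with the two statements that all events are collected.
- **SAP 8.8:** count each Subject once per event category, so that separate records do not inflate rates, and report event counts alongside.
- **Protocol 8.2 and any outcome summary under SAP 8.8:** keep an outcome of not resolved at closure distinct from resolved.

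The cost is somewhat more data entry and adjudication, plus any form fields not already present, which cannot be judged without the case report forms. Reported adverse event rates will be slightly less favourable.

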8.1. Adverse Event Reporting

The Investigator will monitor the occurrence of adverse events for each enrolled Subject. Adverse events reported by the Subject to the Investigator, confirmed by the Investigator, and documented in medical records must be reported on the adverse event form based on the requirements of the study CIP.

All Adverse Events, all Serious Adverse Events, and all Unanticipated Adverse Device Effects will be reported to all Investigators and IRBs and/or Ethics Committees participating in the study

per their reporting requirements. This is done by means of an interim report or a final study report prepared by the Sponsor.

8.2. Adverse Event Outcome Status

Adverse Events, when reported, are assigned a status by centers depending on the nature of the event or the corrective action involved. When clinically appropriate, centers should work to close events whose underlying clinical condition may not be resolvable during the term of the investigation.

Centers may move outcome status to “closed” or alternatively, add text to the adverse event description at a follow-up visit addressing that adverse event stating that the adverse event is ongoing but for study purposes and outcome data, the event is considered closed.

8.3. Device Deficiencies

A **device deficiency** is an inadequacy of a medical device with respect to its identity, quality, durability, reliability, safety or performance. All suspected investigational device deficiencies should be documented on the appropriate CRF. The Sponsor will investigate all suspected device deficiencies.

Note: a device deficiency can include a device malfunction (i.e.: failure to perform to specifications), and may also include other deficiencies (e.g.: ambiguity of labelling).

For the implanted components of ReActiv8, note that not all device deficiencies will lead to an explant. For example, loss of stimulation on one electrode may be resolved by reprogramming such that stimulation can be delivered on a different set of electrodes. Thus a device deficiency may not necessarily lead to an AE or SAE.

If possible, a device with a suspected malfunction should be returned to Mainstay for analysis, including any explanted components. If it is not possible to return the device, the reason it could not be returned as well as its final disposition should be documented.

Note that reporting of device deficiencies shall be separate from adverse event reporting. If there should be an adverse event associated with the device deficiency, then that adverse event should be reported on an adverse event CRF.

8.4. Subject Deaths

A Subject death during the study should be reported to the Sponsor as soon as possible and, in any event, within two working days of notification to the Investigator. The center’s IRB or Ethics Committee must be notified of any deaths in accordance with that center’s IRB or Ethics Committee policies and procedures.

Notification of death should include a detailed narrative (death letter) that provides detailed information describing the circumstances surrounding the death and is signed by the principal Investigator or authorized Sub-Investigator. The death letter should include all of the following:

- Date and time of death
- Place death occurred
- Immediate cause of death
- Whether or not the death was witnessed
- Device status and/or activity at the time of death, if known
- Any other circumstances surrounding the death

9. Data Management

9.1. Study Assessments

The Sponsor will be responsible for collection of the data required for this study in accordance with record and reporting requirements listed in FDA 21CFR812 and Part 11. The Sponsor will use an electronic clinical database which shall have written procedures and document requirements. The Sponsor or its designated CRO(s) will verify and validate that the requirements for an electronic data system to receive and process data can be consistently met. Security, reliability, consistency of the data will be maintained throughout the study. Electronic CRF's will be used on this study. Only those staff at each site that are identified and designated by the Investigator and trained on eCRF data entry system will be allowed access to the eCRF system. Any study assessment questionnaires that required the Subject to complete directly, will be done on paper CRF's then transferred to the eCRF system by the designated study site personnel.

The electronic case report forms, and paper CRFs will reflect the contents of this study protocol. The CRF's and any amendment to them will bear a version date and each page will be identifiable by the study, site and Subject identification numbers. If it is necessary to amend the CRF's, the Sponsor will review the study protocol to determine whether or not an amendment to the protocol is necessary. Study assessments may be recorded using paper notes from which data are transcribed into the eCRF, may include data recorded as per institutional practice (hard copy or electronic), or may be recorded directly into the eCRF, as appropriate.

9.1.1. Medical History

Medical history collected will include characteristics of the Subject's low back pain such as diagnosis and duration, as well as number of episodes of low back pain as well as the medications and procedures for treatment of low back pain that the Subject has failed.

The medical history will include baseline demographics as well as a small set of clinical data that would be collected at a typical visit to a general practitioner.

Collection Method: Information transferred to paper CRFs or eCRF

9.1.2. Subject Screening/Baseline

Subject baseline and screening data collected shall include basic information (e.g., Subject identifier, date of enrollment, etc.) as well as a review of inclusion criteria, and a review of exclusion criteria.

Additional data such as results of a pregnancy test (if applicable) and MRI shall be recorded as per institutional practice and the results included in the eCRF.

Collection Method: Information transferred to paper CRF or eCRF if part of the site source documents.

9.1.3. Depression Anxiety Stress Scale (DASS₂₁)

The DASS₂₁ is a paper questionnaire completed by the Subject alone and without assistance and results are recorded in the eCRF. Validated language specific versions are available.

Collection method: Completed by the Subject on a paper questionnaire then transferred to the CRF or eCRF.

9.1.4. Surgical Procedure

Surgical procedure data collected shall include relevant information during and following the procedure.

Collection Method: Transferred from source documents and surgery worksheets to paper CRF or eCRF

9.1.5. Post-Operative Evaluation

Evaluation of Subject post-operative status will be collected at the Post-Implant Follow-up.

Collection Method: Transferred from source documents to paper CRF or eCRF

9.1.6. Physical Exam and Surgical Site Exam (Post Implant)

After implant, inspect the surgical site and note if healing is normal and as expected. Other elements of the physical exam include weight and information on any new clinical conditions not associated with the Trial.

Collection Method: Transferred from source documents to paper CRF or eCRF

9.1.7. Oswestry Disability Index

The Oswestry Disability Index is a paper questionnaire completed by the Subject alone and without assistance and results are recorded in the eCRF. Validated language specific versions are available.

Collection method: Completed by the Subject on a paper questionnaire then transferred to the CRF

